4.5.5 Subgroup Analyses

The primary and key secondary endpoints (time to onset of 12- and 24 week CDP, change in 25-foot timed walk from baseline to Week 120, and change in total volume of T2 lesions, respectively) will be summarized by the following subgroups:

- Age (≤ 45 vs. > 45 years)
- Sex (male patients vs. female patients)
- Baseline EDSS (≤ 5.5 vs. > 5.5)
- Region (U.S. vs. ROW)
- Presence or absence of gadolinium-enhancing lesions at baseline MRI scan

- Prior MS disease-modifying therapies, with the exception of corticosteroids (yes vs. no)
- Duration since MS symptom onset (≤ 3 years, 3 to ≤ 5 years, 5 to ≤ 10 years, > 10 years)
- Weight (≤ 75 vs. > 75 kg at baseline)
- Body mass index (< 25 vs. ≥ 25 kg/m², at baseline)

4.6 PHARMACOKINETIC AND PHARMACODYNAMIC ANALYSES

4.6.1 Pharmacokinetic Analyses

Nonlinear mixed effects modeling will be used to analyze the sparse sampling dose–concentration–time data of ocrelizumab. Patients who have measurable concentrations of ocrelizumab will be included in the PK analysis unless major protocol deviations or the unavailability of information (e.g., exact blood sampling time) occur that may interfere with PK evaluation. The PK data from this study may be pooled with other studies. Population PK parameters (clearances and volumes) will be estimated, and the influence of covariates such as age, sex, weight, ADAs, and baseline CD19⁺ lymphocytes on these parameters will be investigated.

The model developed based on relapsing multiple sclerosis (RMS) data will be used to predict PK profiles in the PPMS study. If predictions match observations, this population PK model based on RMS data will be deemed acceptable to describe the PK in PPMS patients too. If predictions do not match observations, a population PK model based on the PPMS or pooled RMS+PPMS data will be developed.

Details of the mixed effects modeling analyses will be described in a Modeling and Simulation Analysis Plan, and results will be reported separately.

4.6.2 Pharmacodynamic Analyses

If possible, nonlinear mixed effects modeling will be used to investigate the relationship between ocrelizumab exposure and selected safety and efficacy parameters.

Exploratory analyses may be performed to assess the possible relationship between PD markers like B cells, pharmacokinetics, and clinical response; this will be described in a Modeling and Simulation Analysis Plan, and results will be reported separately.

4.7 SAFETY ANALYSES

The safety population is defined in Section 4.1.3. All safety parameters will be summarized and presented in tables on the basis of this safety population. Randomized patients who receive incorrect therapy will be summarized in the group according to the rules laid out in Section 4.1.3. Placebo patients who received any ocrelizumab in error will be assigned to the ocrelizumab group.

Patients who are not randomized but who receive study drug will be included in the safety population and summarized according to the therapy actually received.

This SAP describes the analyses of all available safety data collected until the end of the trial. The safety data will be summarized descriptively for the DBP, ECP, OLE and SFU periods.

4.7.1 Exposure of Study Drug

The amount of ocrelizumab or placebo infused at each infusion will be listed and summarized using descriptive statistics.

Definition of dose: A dose of ocrelizumab is given as two infusions administered 2 weeks apart.

Patients will be considered to have received a dose of treatment if at least part of one infusion of that dose (either Day 1 or Day 15 for dual infusions) was given. If a dose is completely missed instead of delayed, the next dose number will be based on the number of previous doses received.

The duration of observation for a patient will be calculated as follows:

$(\text{Date of last contact}^* - \text{Date of first infusion in the first dose}) + 1$

*Earliest 1) date of CCOD for the primary analysis reporting; 2) date of subject completed or discontinued early from the study completion end of study page; or 3) date of death.

The duration of observation, within a dose, is defined in a similar manner as follows:

$(\text{Day prior to first infusion in the } n + 1\text{th dose}^* - \text{Date of first infusion in the } n^{\text{th}}\text{ dose}) + 1$

*With the exception of the last dose received by the patient where the date of last contact is used as defined above. If the last contact is after the date of the clinical cutoff, the date of last contact will be the CCOD.

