The study has been unblinded at the end of the blinded treatment period in September 2015 (clinical cutoff date [CCOD] 24 July 2015) when reaching at least 120 weeks after the last patient randomized provided that the planned number of confirmed disability progression (CDP) has reached 253, (number of events included in the primary analysis: 256). After the positive readout, patients were given access to the OLE starting from 12 October 2015. In the period between the CCOD for the Primary CSR and OLE initiation, the Sponsor, sites, and patients were sequentially unblinded. This period corresponds to the Extended Controlled treatment period (ECP).

encompasses all efficacy data from the double-blind period (DBP) (previously reported in the Primary CSR) plus any additional efficacy data collected during the controlled treatment period up to the time at which the patient received their first open-label dose of ocrelizumab or until withdrawal.

This document has been updated (Version 5) to describe the further analyses to be performed, on:

1. the ECP, including additional data collected after the primary CCOD up to the entry into OLE.
2. the OLE period, including additional data collected from the first dose of Ocrelizumab in OLE.
3. the combined periods of ECP and OLE.

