Percent change in cortical gray matter volume from Week 24			X
Percent change in white matter volume from Baseline		X	X
Percent change in white matter volume from Week 24			X
Annualized Percentage Change in T1 lesion volume from Baseline to OLE end during the Extended Controlled Treatment and OLE Period		X	X
Annualized Percentage Change in T2 lesion volume from Baseline to OLE end during the Extended Controlled Treatment and OLE Period		X	X
Annualized Percentage Change in Total Brain Volume from Baseline to OLE end during the Extended Controlled Treatment and OLE Period		X	X
Annualized Percentage Change in Cortical Grey Matter Volume from Baseline to OLE end during the Extended Controlled Treatment and OLE Period		X	X
Annualized Percentage Change in White Matter Volume from Baseline to OLE end during the Extended Controlled Treatment and OLE Period		X	X
Descriptive statistics: SF-36, MFIS, NfL			X
Safety Summary: Additional safety data collected during ECP and OLE	X	X	X

9-HPT = 9-hole peg test; ECP = extended controlled treatment period; EDSS = Expanded Disability Status Scale; ITT = intent-to-treat; MFIS = Modified Fatigue Impact Scale; MMRM = Mixed-Effect Model Repeated Measures; MRI = magnetic resonance imaging; MSFCS = Multiple Sclerosis Functional Composite Scale; NfL = Neurofilament Light chain; OLE = open-label extension; T25-FW = timed 25-foot walk.

All analyses performed for the primary CSR are included in this statistical analyses plan. In general, the analyses performed on the extension periods follow the same analyses rules as for the primary CSR. Exceptions have been added in the respective sections.

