5. The study originally planned to enroll approximately 630 patients who were to be followed for at least 120 weeks. The study actually enrolled 732 patients (last patient enrolled on 27 December 2012). To explore the effect of the higher enrollment number, the analysis of the primary efficacy endpoint will be performed using the first 630 patients on the basis of their randomization dates (ITT population) at the time of the primary analysis.
6. The primary analysis described above will be adjusted with additional strata for the baseline presence of gadolinium-enhancing T1 lesions (present or absent) and baseline EDSS (≤ 5.5 vs. > 5.5).
7. PPMS is characterized by a progressive course from disease onset typically without superimposed discrete clinical attacks or relapses (Ebers 2004). The primary analysis on CDP for ≥ 12 weeks, described above will be performed excluding patients who have any clinical relapses during the study. Clinical relapses include protocol-defined relapses.
8. For the time to onset of CDP for ≥ 24 weeks, the influence of early progression events on treatment effect will also be evaluated by omitting the EDSS assessments performed between randomization and the Week 12 visit (≤ 83 days after randomization) with use of the ITT population.
9. For the time to onset of CDP for ≥ 24 weeks, the analysis will be performed excluding patients who have any clinical relapses during the blinded treatment period.

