4.7.6 Clinical Genotyping

The following genetic markers will be summarized descriptively. A summary of polymorphism ID, genotype frequency, and allele frequency will be generated:

- RO_000052326 (FCGR2A)
- RO_000059393 (FCGR3A)

The frequency of HLA-DRB1 positive assessments at baseline will be summarized.

Additionally, a summary of occurrence of AEs for <GENE> by genotype frequency for MS relapses, infections and IRRs will be generated for the same genetic markers.

Extended Periods

Above summaries and listings of safety assessments will be repeated for the ECP and OLE periods (including the SFU after withdrawal from ECP or OLE treatment).

These include but are not limited to;

- AEs leading to withdrawal from treatment and AEs leading to dose modifications
- Malignancies
- Serious infections
- Deaths
- IRRs by visit
- Summary of safety laboratory assessments, vital signs, antibody titers, immunoglobulins by visit
- Summary of treatment emergent ADAs
- Listing of pregnancy information

For OLE summaries, data will be presented as defined in OLE Safety Population.

Analyses pooling all safety data from the first dose of ocrelizumab (ECP and OLE periods) across multiple MS trials are described separately in a Global Safety Pooling SAP.

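### SAP 4.7.1 still caps safety observation at the primary cut-off (24 July 2015), so patient-time for extension and final reporting is truncated, and last-dose durations turn negative for OLE patients

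*SAP*

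**What the plan says.** SAP 4.7.1 (Exposure of Study Drug) calculates duration of observation as date of last contact minus date of first infusion in the first dose, plus 1. Last contact is the "Earliest 1) date of CCOD for the primary analysis reporting; 2) date of subject completed or discontinued early" from the study, or 3) death. For time within a dose, each dose runs to the day before the next one. The last dose runs to the date of last contact, with the added rule: "If the last contact is after the date of the clinical cutoff, the date of last contact will be the CCOD".

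SAP Section 1 gives the primary cut-off as "clinical cutoff date [CCOD] 24 July 2015". The reporting table in SAP 2.3 lists that date for the primary report only, then 20 January 2016, 3 January 2020 and a final report after 31 December 2022.

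Version 5 was written to cover the extended controlled period (ECP) and the OLE. SAP 4.2 states: "In general, the analyses performed on the extension periods follow the same analyses rules as for the primary CSR", and adds that exceptions appear in the sections concerned. Section 4.7.1 contains none. SAP 4.7 says "This SAP describes the analyses of all available safety data collected until the end of the trial". The Extended Periods paragraph at the end of SAP 4.7.6 says "Above summaries and listings of safety assessments will be repeated for the ECP and OLE periods", including safety follow-up (SFU) after withdrawal from either.

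SAP 4.7.2 uses patient-years as the denominator for rates of adverse events, serious adverse events, infections, serious infections, opportunistic infections and malignancies. It reports these by treatment, and by treatment and dose.

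**The concern.** The denominator has a fixed end in July 2015, while the safety data in scope run to the end of 2022. No sentence in SAP 4.7.2 applies a matching end date to the events. Taken as written, events from up to seven further years would be divided by patient-time that stops at the primary cut-off. The exact confidence limits in 4.7.2 divide by the same patient-years, so they would shift with the rate.

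Rates by dose are affected in a second way. SAP 4.7.2 assigns events during SFU to the last dose received, and the last dose is the one whose duration uses the capped date.

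At stake are the exposure-adjusted rates for the extension and the final report. The primary report is not at risk, because 24 July 2015 is its correct cut-off.

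**Working it through.** The SAP gives no patient-years figure to reproduce, so the check applies the 4.7.1 formula to dates in the documents.

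**Inputs**
- Primary cut-off: 24 July 2015 (SAP 1 and 2.3).
- Earliest OLE entry: "patients were given access to the OLE starting from 12 October 2015" (SAP 1).
- Latest start of blinded treatment: "last patient enrolled on 27 December 2012" (SAP 4.5.4), assuming the first infusion was on that day.
- End of study: 31 December 2022 (SAP 2.3).

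**Total observation, last patient enrolled, followed to study end**
- As written: 24 Jul 2015 − 27 Dec 2012 + 1 = 940 days (2.57 years).
- With the final cut-off: 31 Dec 2022 − 27 Dec 2012 + 1 = 3657 days (10.01 years).
- Lost: 1 − 940/3657 = 74%. If this patient's events were counted to 2022 at a constant rate, the rate would be overstated by 3657/940 = 3.9.
- For patients assumed to start 12 or 18 months earlier and also followed to the end, the ratios are 4023/1306 = 3.1 and 4206/1489 = 2.8.

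**Last-dose duration, any patient dosed in the OLE**
- The last dose is on or after 12 October 2015, and last contact is capped at 24 July 2015. The result is at most 24 Jul 2015 − 12 Oct 2015 + 1 = −79 days.
- With an assumed last dose on 1 July 2022: 24 Jul 2015 − 1 Jul 2022 + 1 = −2533 days (−6.9 years).

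**Non-final doses**
- These end the day before the next dose and carry no cap. Take the last patient enrolled on an assumed 24-week schedule: six blinded doses, then OLE doses from 12 October 2015 to 5 September 2022, 22 doses in all. The 21 non-final durations are 20 × 168 + 179 = 3539 days, and the last is −2599 days. The sum is 3539 − 2599 = 940, the capped total.

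**OLE-only duration**
- 4.7.1 names no OLE start. If the clock starts at the first OLE infusion, the earliest entrant has −79 days and later entrants have less. If it starts at the first blinded infusion, as literally written, the value is positive but consists wholly of time before the OLE.
- With the final cut-off, the earliest entrant followed to study end has 31 Dec 2022 − 12 Oct 2015 + 1 = 2638 days (7.22 years).

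**Whole trial, illustration only**
- Mean time to the cut-off, m: 2.57 years plus half of the planned accrual of 1 year (SAP 2.2) to 1.5 years (Protocol 4.1.2) = 3.07 to 3.32 years, ignoring early exits.
- Time from cut-off to study end: 7.44 years.
- Assume that a fraction f = 0.5 to 0.7 of patients adds e = 2 to 7.44 years each. The ratio of true to credited time is 1 + f·e/m. Low: 1 + 0.5 × 2/3.32 = 1.3. High: 1 + 0.7 × 7.44/3.07 = 2.7.

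**The case against.** The best defence is that item 1 names the primary analysis because it was written for that report and then left in place. SAP 2.3 gives each report its own cut-off. Its period definitions run the OLE and combined periods to study completion or withdrawal from treatment. The last-dose note speaks of the clinical cut-off without naming a report. An analyst could well use the right date, and negative patient-time would be noticed in programming.

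As an account of intent this is plausible. It does not settle the text. No sentence supplies another cut-off for the formula. The last-dose rule reuses the same definition of last contact, and the period definitions in 2.3 conflict with the formula without replacing it. Where a rule did change after the primary report, the SAP says so: 4.7.2.2 gives separate definitions of serious infection for the primary report and for later ones. Section 4.7 also still refers to 4.1.3 for the safety population, which in Version 5 is the per-protocol population, so incomplete updating is the likely explanation.

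Other parts of the objection stand. A reader might infer that every patient's observation stops in July 2015, or that all extension durations are negative. The documents do not support that. Patients who left or died earlier keep their own end date, non-final dose durations are not capped, and ECP and whole-study totals are shortened but positive. The −79 days for an OLE-only duration also requires the start to be moved to the first OLE infusion, which 4.7.1 does not instruct. On a fully literal reading only the last-dose duration is negative.

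**Conclusion.** The rule is wrong as written for any report after the primary one. For patients still in the study on 24 July 2015, total observation is truncated; the documents' dates give 940 instead of 3657 days for the last patient enrolled, if dosed on the enrolment date and followed to study end. Last-dose durations are negative for all patients dosed in the OLE. Rates that count extension events over this denominator would be overstated.

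The factor of 1.3 to 2.7 is not an estimate of the trial's actual error, because retention and added follow-up are assumed and the accrual period is the planned one. A reader might also infer that the plan would create a false signal of rising risk for late events such as malignancy. The documents do not show that. The calculation assumes a constant rate, and the inflation arises only if events are counted past the date where patient-time stops. SAP 4.7 points that way but does not spell out the event window. Capping events at the same date would remove the inflation but discard the extension data that 4.7 and 4.7.6 say will be analysed.

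The Extended Periods list does not name rates per 100 patient-years, but it repeats the summaries above it and is expressly not exhaustive. Pooled analyses across studies follow a separate plan that is not available here.

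**What to change.** In SAP 4.7.1, replace the primary-analysis cut-off in item 1 with the CCOD of the respective reporting event (for the final report, the end of study), and use the same date in the last-dose rule.

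State the start and stop of patient-time for each reporting period, consistent with the period definitions in SAP 2.3, with the OLE starting at the first OLE infusion. Say that events and patient-time are counted over the same window.

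The treatment of SFU must be settled at the same time. The Version 5 rationale analyses OLE and OLE SFU separately, and SAP 4.7 lists SFU as a period of its own, while the Extended Periods paragraph in 4.7.6 includes SFU with the ECP and OLE. The OLE period in SAP 2.3 also stops at withdrawal from treatment. The text should say whether SFU time and events belong within the ECP and OLE or are reported apart, and apply that to numerator and denominator alike.

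The cost is SAP wording and one derivation in the exposure dataset. No new data are needed, and the primary report does not change.

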4.7.2 Adverse Events

Adverse events (AEs) will be defined as all AEs including infusion-related reactions (IRRs) and serious MS relapses, but excluding non-serious MS relapses. Therefore, those AEs recorded on the AE and IRR CRF pages will be included. Refer to Section [4.7.2.5](#) for further guidance on MS relapses considered SAEs.

For each recorded AE, the term entered by the investigator describing the event (the “reported term”) will be assigned a standardized term (the “Preferred Term” [PT]) and assigned to a superclass term on the basis of the MedDRA World Health Organization

(WHO) dictionary of terms. All analyses of AE data will be performed using the PTs unless otherwise specified.

For all summary tables, the AEs will be sorted by System Organ Class (SOC; in decreasing order of overall incidence) and then by PT (in decreasing order of overall incidence). All summaries and listings of AEs will be based on the safety population, unless stated otherwise. Summaries of AEs will be generated to summarize the incidence of treatment emergent AEs only. Treatment Emergent events are defined as those AEs with an observed or imputed date of onset on or after the start date of trial treatment. If the onset date of the AE is prior to the day of first dose, the AE will be considered treatment emergent only if the most extreme intensity is greater than the initial intensity (i.e., the intensity for a given AE increases and its end date is on or after the date of the first dose). An AE with a completely missing, nonimputed start date will be assumed to be treatment emergent unless the AE has a complete, nonimputed end date that is prior to the date of the first dose.

AEs will be assigned to a dose if the AE onset date is on or after the date of the first infusion of that dose but before the first infusion of the next treatment dose. AEs that are reported during the SFU period (including the B-cell monitoring period) will be assigned to the last dose received. Hence, the last dose for a patient may be of a variable length, from 24 to 72 weeks or longer. AEs that start prior to the first dose and worsen during treatment (i.e., treatment-emergent) will be assigned to the first treatment dose.

The number of patients who experienced a related AE will be summarized by SOC and PT. AEs will be summarized by SOC and PT by intensity grade. Multiple occurrences of the same event within a patient will be counted once at the greatest intensity/highest grade for this PT. For AEs leading to death, the most extreme intensity will be overwritten by Grade 5 (death). Any AEs and the SOC overall rows of the summary table will count patients according to AEs by intensity (grade).

All patient deaths, regardless of treatment received, will be listed.

SAEs will be defined as all SAEs including serious MS relapses and serious IRRs. The number of patients who experienced an SAE will be summarized by SOC and PT. Related SAEs will be summarized by SOC and PT. Additionally, the most frequent SAEs ($\geq 1\%$) will be presented by PT.

A patient may experience an AE that leads to the discontinuation of his/her study treatment. Discontinuation of study treatment for an AE may not necessarily lead to discontinuation from the study because the patient can enter the SFU period of the protocol. Only AEs that led to the discontinuation of study treatment are of interest. Patients who withdraw early from the study because of AEs will be summarized under disposition. The number of patients who experienced an AE that led to discontinuation of study treatment will be summarized by SOC and PT. The number of patients who

experienced an AE that led to modification or interruption of study drug will be summarized by SOC and PT.

For each treatment group, the incidence count for each AE PT will be defined as the number of patients reporting at least one treatment emergent occurrence of the event. The incidence rate will be calculated as the incidence count divided by the total number of patients in the population. Each table will also present the overall number of patients experiencing at least one AE and the total number of AEs reported (multiple occurrences of the same AE in 1 patient will be counted only once).

The rate per 100 patient-years by treatment group (along with the 95% CI) will be calculated for specific events of interest such as all AEs, SAEs, infections and serious infections, opportunistic infections (OIs), and malignancies (see Section 4.7.2.2, Section 4.7.2.3 and Section 4.7.2.4, respectively).

- The number of AEs per 100 patient-years is calculated as:

Total number of AEs / Total number of patient-years \times 100

- The 95% CI for the number of AEs per 100 patient-years is calculated as follows (Sahai and Kurshid 1993):

Exact lower 95% confidence limit = $\text{chisq}(p=0.025, df=2Y) / (2T)$

Exact upper 95% confidence limit = $\text{chisq}[p=0.975, df=2(Y+1)] / (2T)$

where Y is the total number of AEs, T is total number of patient-years at risk and $\text{chisq}(p,df)$ is the quantile of the upper tail probability of the X^2 distribution on df (degrees of freedom). This approach has the advantage of providing an estimate for the upper 95% confidence limit even when the total number of AEs is zero.

The rates per 100 patient-years will be summarized by treatment and dose and by treatment (including all doses).

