4.7.2.3 Opportunistic Infections

Opportunistic infections (OIs) will be defined using the Ocrelizumab specific MedDRA Term Selection (MTS) basket of “Opportunistic infections.”

The number of patients who experienced an OI will be summarized by SOC and PT.

The rate per 100 patient-years by treatment group (along with the 95% CI) will be calculated for OIs overall.

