4.7.2.4 Malignancies

Malignancy and pre-malignancy AEs will be identified using the standard MedDRA query (SMQ) of “Malignant tumours (narrow)” and “Pre-malignant disorders,” respectively.

The number of patients with a malignancy will be summarized by SOC and PT. The pre-malignancy AEs will be listed.

The rate per 100 patient-years by treatment group (along with the 95% CI) will be calculated for malignancies.

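### SAP 4.7.2: the exact 95% CI for adverse event rates per 100 patient-years names the wrong chi-square tail and leaves out the factor of 100

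*SAP*

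**What the plan says.** SAP 4.7.2 (Adverse Events) defines the rate as "Total number of AEs / Total number of patient-years", multiplied by 100. It then introduces the interval: "The 95% CI for the number of AEs per 100 patient-years is calculated as follows". With Y the number of events and T the patient-years at risk, the limits printed are:

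- lower: chisq(p = 0.025, df = 2Y) / (2T)
- upper: chisq(p = 0.975, df = 2(Y+1)) / (2T)

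The function is then explained: chisq(p, df) "is the quantile of the upper tail probability of the" chi-square distribution. The reason given for the method is its behaviour with no events: "This approach has the advantage of providing an estimate for the upper 95% confidence limit even when the total number of AEs is zero".

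The interval serves all AEs, SAEs, infections, serious infections, opportunistic infections and malignancies (4.7.2, 4.7.2.2 to 4.7.2.4). Rates are tabulated by treatment, and also by treatment and dose. On use, SAP 4.7 says: "The safety data will be summarized descriptively for the DBP, ECP, OLE and SFU periods".

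**The concern.** Two things in this specification do not fit together.

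- **Tail.** An upper-tail quantile at p = 0.025 is a large number and at p = 0.975 a small one. The printed p values therefore put the large quantile in the lower limit and the small one in the upper limit.
- **Scale.** The estimate is per 100 patient-years, T is in patient-years, and neither limit carries the factor of 100.

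No other part of the SAP restates or corrects the formula. The sample SAS code covers efficacy models only.

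The zero-event case matters most. There the upper limit is the only figure that shows how large a risk the data still allow, and it is the case the SAP cites in favour of the method. Zero counts are plausible for sparse events. Protocol 7.3.1.1 reports no opportunistic infections in ocrelizumab-treated MS participants during the controlled period of the pivotal trials. The SAP identifies these infections by its own MedDRA basket, however, so a zero in its tables is possible but not established.

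**Working it through.** The SAP gives a formula and no numerical interval, so there is no stated figure to reproduce. The intervals per 100 patient-years in Protocol 2.1.4.1 come from the Phase II study and cannot test this formula. The inputs are the rate, the two limits and the definitions of T and chisq, all from SAP 4.7.2. The value T = 1000 patient-years is an illustrative assumption.

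**1. Which tail gives the exact interval.** Exact 95% limits L and U for a Poisson mean satisfy P(X ≥ Y | L) = 0.025 and P(X ≤ Y | U) = 0.025. With lower-tail quantiles, L = chisq(0.025, 2Y)/2 and U = chisq(0.975, 2Y+2)/2. Putting these back into the Poisson tails gives 0.025 on both sides at Y = 1, 5 and 10. The printed p values and degrees of freedom are therefore right for the lower tail and wrong for the upper tail.

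**2. Zero events, tail error alone.** With 2 degrees of freedom the chi-square is exponential with mean 2.

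- Upper tail, as written: −2 ln(0.975) = 0.0506, so the limit is 0.0506/(2T) = 0.0253/T per patient-year.
- Lower tail: −2 ln(0.025) = 7.378, so the limit is 7.378/(2T) = 3.689/T per patient-year.
- Ratio: 7.378/0.0506 = 145.7 (from unrounded quantiles), whatever T is.

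**3. One or more events, tail error.** At Y = 1 the written lower limit uses 7.378 (2 df) and the written upper limit uses 0.484 (4 df). The lower limit exceeds the upper at every Y from 1 to 20,000.

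**4. Scale error alone.** With the right tail but no factor of 100, the upper limit divided by the rate is [chisq(0.975, 2Y+2)/(2T)] / (100Y/T). At Y = 1 and T = 1000 this is 0.00557/0.10 = 5.6%, the largest value for Y from 1 to 20,000. The interval therefore lies entirely below its own estimate throughout that range.

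**5. Both errors at zero events.** 145.7 × 100 = 14,570.

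**6. Examples at T = 1000 patient-years.**

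| Y | Rate per 100 PY | Exactly as printed (lower; upper) | Right tail, no ×100 | Right tail, ×100 |
|---|---|---|---|---|
| 0 | 0 | lower has df = 0; upper 0.000025 | upper 0.00369 | 0 to 0.369 |
| 1 | 0.10 | 0.00369; 0.00024 | 0.000025 to 0.00557 | 0.0025 to 0.557 |
| 10 | 1.00 | 0.0171; 0.0055 | 0.0048 to 0.0184 | 0.480 to 1.839 |
| 100 | 10.0 | 0.1205; 0.0823 | 0.0814 to 0.1216 | 8.14 to 12.16 |

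The third column applies the text with nothing restored. The last column is the intended interval.

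**The case against.** The strongest reply is that the intended method is plain. The limits are labelled exact, carry the right p values and degrees of freedom, cite a published method, and are introduced as per 100 patient-years. Only the tail phrase conflicts with this. A programmer using a standard cumulative quantile function would get correctly ordered limits. The SAP's amendment history (Version 2) also says the derivation was aligned with the Phase III RMS studies, so it need not have been built from this sentence alone. Errors would show: limits would invert in every row with events, and without the factor of 100 each non-zero rate would fall outside its interval. The use is descriptive, with no test or decision rule attached.

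Most of this stands, and it limits the consequences. It does not make the text correct. This is the SAP's only specification of the interval, and an independent program written from it would not agree with a correct one.

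Three stronger readings are tempting, and the documents do not support them.

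- A reader might infer that reported safety intervals are wrong. The documents show no limit computed with this formula.
- A reader might infer that the zero-event error would pass unseen. A single zero-event row shows nothing odd, but the same formula fills rows with many events, where the inversion would be visible.
- A reader might take 146 as the combined effect. It is the tail error alone.

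**Conclusion.** The formula is wrong as written in two separate respects, and no other text in the SAP corrects either. The tail error inverts the limits at every count from 1 to 20,000 and makes the zero-event upper limit 146 times too small. The scale error leaves both limits 100 times too small for the rate they accompany. Together they make the zero-event upper limit about 14,570 times too small. These factors do not depend on T; only the worked limits rest on the assumed 1000 patient-years.

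This is a specification error confined to descriptive safety rate intervals. Efficacy analyses, event counts, person-time and the rates themselves are untouched, and no effect on reported results is shown.

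**What to change.** Restate the limits in SAP 4.7.2 as:

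- lower = 100 × chisq(0.025, 2Y)/(2T), set to 0 when Y = 0
- upper = 100 × chisq(0.975, 2(Y+1))/(2T)
- chisq(p, df) = the lower-tail (cumulative) quantile of the chi-square distribution

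Keeping the upper-tail definition and exchanging the two p values would be equivalent. Exchanging the two printed limits would not, because the degrees of freedom would then sit on the wrong limits: at Y = 10 and T = 1000 it gives 0.549 to 1.708 per 100 patient-years after scaling, against 0.480 to 1.839.

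Then check that completed outputs, including the primary CSR, and the programs for the final CSR (listed as planned in SAP 2.3) use the corrected form. The cost is a short wording change and a check of programs and tables. The method and the data stay as planned.
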